6.6.2 Dose-limiting Toxicities – Definition and Criteria

A DLT is defined as any of the following AEs according to the National Cancer Institute Common Terminology Criteria for Adverse Events (NCI-CTCAE) Version 5.0 assessed by the Investigator and/or the Sponsor at any dose, judged not to be related to the underlying disease or any previous or concomitant medication or concurrent condition, occurring during the DLT observation period, which for Part 1A starts on the first day of study intervention (Day 1) and has a duration of 21 days.

Study accrual will be halted, pending discussions with the SMC or the study Sponsor, if there is an occurrence of a Grade 5 toxicity by the NCI-CTCAE Version 5.0 attributable to the treatment regimen or if more than 1 DLT is seen in DL 1 in Part 1A.

The treatment of toxicities with transfusions or growth factors (e.g., granulocyte-colony stimulating factor, erythropoietin) is not permitted during the DLT period and if it occurs will be considered a DLT.

AEs judged as DLT will include:

- Any Grade ≥ 3 non-hematologic AE with exception of:
 - Single laboratory values out of normal range that have no clinical correlate and resolve to Grade ≤ 1 or to baseline within 7 days with adequate medical management or asymptomatic Grade 3 lipase or amylase elevation (> 5 ULN) not associated with clinical manifestation of pancreatitis.
 - Infusion-related reaction resolving within 6 hours from the end of infusion and controlled with medical management (for iv compounds only)
 - Diarrhea persisting < 72 hours after initiation of medical management
 - Nausea and vomiting of ≤ 72 h duration with adequate and optimal therapy
 - Transient (≤ 72 h) fatigue, local reactions, flu-like symptoms, fever, headache, hypertension that resolves to Grade ≤ 1 with adequate treatment
 - Grade 3 non-recurrent skin toxicity that resolves to Grade ≤ 1 in less than 7 days after initiation of medical management
 - Tumor flare phenomenon defined as local pain, irritation, or rash localized at sites of known or suspected tumor that resolve to Grade ≤ 2 within 6 days
 - Any death clearly due to the underlying disease or extraneous causes

- Grade ≥ 3 neutropenia with clinical signs/symptoms, such as fever $> 38.5^{\circ}\text{C}$ (e.g., for febrile neutropenia, an ANC $< 1000/\text{mm}^3$ with single temp of 38.3°C [101°F] or a sustained temperature of $\geq 38^{\circ}\text{C}$ [100.4°F] for more than one hour)

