- Grade ≥ 3 thrombocytopenia with medically concerning bleeding
- Any Grade ≥ 4 hematologic AE, except:
 - Isolated Grade 4 lymphopenia without clinical correlate
 - Any Grade 4 neutropenia of < 7 days' duration not associated with any clinical symptoms
- All events of ALT $\geq 3 \times$ upper limit of normal (ULN) and bilirubin $\geq 2 \times$ ULN ($> 35\%$ direct bilirubin) or ALT $> 3 \times$ ULN and international normalized ratio (INR) > 1.5 , if INR measured, may indicate potential severe liver injury (possible Hy's Law), will require prompt permanent discontinuation from the study, and will be reported as an SAE (excluding studies of hepatic impairment or cirrhosis):
 - Without initial findings of cholestasis (elevated serum ALP).
 - In the absence of other reasons than drug toxicity to explain the laboratory constellation (e.g., viral hepatitis A, B, C or co-medication).
 - In the absence of other reasons than drug toxicity to explain the laboratory constellation.
- Any AE leading to the inability to deliver at least 80% of the planned total dose for the DLT period, except in situations other than toxicity, e.g. participant noncompliance or logistical issues with study intervention delivery.
- Death not clearly attributed to underlying disease or alternative cause.
- Additionally, the SMC may identify as a DLT:
 - A TEAE (inside or outside of the DLT period) that in the opinion of the SMC is of potential clinical significance such that further dose escalation would expose participants to unacceptable risk

The SMC must confirm any DLT.

If any change is made to the grade or causality of an AE during the study that may alter its DLT status, the Sponsor must be informed immediately as this may affect dose escalation decisions.

Additionally, participants excluded from the DLT analysis set may be replaced; the decision will be made by the SMC.

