8.3.6 Adverse Events of Special Interest

For this study, AESIs include only the following:

- Cytopenia (lymphopenia, leukopenia/neutropenia, thrombocytopenia, anemia), Grade ≥ 3 or with complications, e.g., neutropenia with fever or infection or thrombocytopenia with medically concerning bleeding.

An AESI (serious or nonserious reaction) is one of scientific and medical concern specific to the study intervention, for which ongoing monitoring and rapid communication by the Investigator to the Sponsor is required. Such events of interest may require further investigation or in-depth evaluations to better characterize and understand the association between the AE and M4076. Based on nonclinical data, the following AEs will be considered AESI (Table 11).

Table 11 Adverse Events of Special Interest

AE	Management
Cytopenias (lymphopenia, leuko/neutropenia, thrombocytopenia, anemia), Grade ≥ 3 or with complications, e.g. neutropenia with fever or infection or thrombocytopenia with medically concerning bleeding.	Repeat blood test within 72 hours of receiving the abnormal lab result. Continuous monitoring of AEs with clinical management as indicated, including study intervention interruption, dose modification or discontinuation (see Table 10).

AE = Adverse event.

The Investigator must complete the AESI Report Form and communicate with the Sponsor within 24 hours of occurrence of AESI. Serious AESI (based on SAE reporting criteria) should always be reported as SAE as outlined in Section [8.3.4](#).

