- SAE reporting on a paper report form is used as a back-up method for an EDC system failure. The form includes completion instructions for the Investigator, names, addresses,

and telephone and fax numbers. All information from the paper form will be transcribed into the electronic form as soon as the system becomes available.

- Facsimile transmission (fax to mail) of the paper form or any follow-up information is the preferred method for transmission and will be done within 24 hours to the Sponsor or its designee.
- In rare circumstances and in the absence of facsimile equipment, notification by telephone is acceptable with a copy of the form sent by overnight mail or courier service.
- Initial notification via telephone does not replace the need for the Investigator to complete and sign the form within 24 hours after becoming aware of the event.
- Additional documents (e.g. laboratory reports, autopsy report, hospital discharge letter) and relevant pages from the CRF may be required in addition (e.g. medical history, concomitant medication). The data provided will be consistent with the information in the CRF.

Recording and Reporting of DLTs

- Each event that meets the DLT criteria, as specified in Section 6.6.2, will be recorded in the CRF within 24 hours after awareness of the event.
- Serious DLTs will be reported in an expedited manner, using the SAE reporting process, as specified above.
- Notification of each DLT related event (non-serious and serious) will be reported to the Sponsor or its designee within 24 hours from the date of awareness.

Reporting of AESIs

- For a non-serious AESI, the site will complete the specific AESI report form and notify the Sponsor immediately (within 24 hours), using the same process for reporting SAEs, as specified above.
- For a serious AESI, the site will complete an SAE report form, using the SAE reporting process, specified above.

Reporting of Pregnancies

- Pregnancy will be reported whether related to the study intervention using the applicable paper form.
- The applicable form will be used to report if an abnormal outcome of the pregnancy occurs and the child/fetus sustains an event.
- Facsimile transmission (fax to mail) of the paper form or any follow-up information is the preferred method for transmission and will be done within 24 hours to the Sponsor or its designee.

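### The neutropenia DLT criterion gives two conflicting fever thresholds, so a site could fail to flag Grade 3 neutropenia with fever between them (minor)

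*Protocol*

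**What the plan says.** Protocol Section 6.6.2 lists as a DLT Grade 3 or higher "neutropenia with clinical signs/symptoms, such as fever" above 38.5°C. The same bullet adds a bracketed example, "for febrile neutropenia, an ANC" below 1000/mm³ with a single temperature of 38.3°C [101°F], or a temperature of at least 38°C [100.4°F] lasting more than one hour.

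Other provisions bear on the same patients:

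- **Grade 4 neutropenia (6.6.2).** It is exempt only when it is of under 7 days' "duration not associated with any clinical symptoms". No temperature is set.
- **Who decides (6.6.2).** DLTs are "assessed by the Investigator and/or the Sponsor at any dose", and "The SMC must confirm any DLT". The SMC may also name as a DLT "A TEAE (inside or outside of the DLT period) that in the opinion of the SMC is of potential clinical significance", if further escalation would carry unacceptable risk.
- **AESI (8.3.6).** Grade 3 or higher neutropenia qualifies whatever the temperature, and the investigator "must complete the AESI Report Form and communicate with the Sponsor within 24 hours of occurrence of AESI".
- **Site recording (Appendix 4).** "Each event that meets the DLT criteria, as specified in Section 6.6.2, will be recorded in the CRF within 24 hours" of awareness.
- **SAP Section 15.1.** DLTs are tabulated per investigator, from the flag on the AE CRF page, and per SMC decision. The dose-toxicity models use the SMC decision.

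**The concern.** The example does not fit the threshold it illustrates: both bracketed temperatures lie below 38.5°C. The AESI text mentions neutropenia with fever but gives no temperature, and the SAP does not restate the criterion.

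Occurrence of DLTs is a primary endpoint, and the site makes the first call on whether an event meets Section 6.6.2. That call has three direct consequences:

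- It sets the investigator's DLT flag.
- During the DLT period it triggers the mandatory interruption in Section 6.6.2.1.
- If the SMC has chosen the next dose before the last participant finished, a DLT in that participant triggers the ad-hoc meeting in Section 6.6.1.

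Part 1B uses the same criteria for unacceptable toxicity at any time on treatment (Sections 4.1.2 and 9.4.2.2). Cytopenia is a listed potential risk and the study's only AESI, so the wording concerns a toxicity the sponsor anticipates.

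**Working it through.** There is no stated figure to reproduce. The check compares the temperatures and then traces what else would catch the event.

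**1. Is one figure a misprint of the other?** Using F = 1.8 × C + 32:

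- 38.0°C: 1.8 × 38.0 + 32 = 100.4°F (printed 100.4°F)
- 38.3°C: 1.8 × 38.3 + 32 = 100.94°F (printed 101°F)
- 38.5°C: 1.8 × 38.5 + 32 = 101.3°F (not printed)

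The printed Fahrenheit values match 38.0 and 38.3, so the lower figures are intended.

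**2. Where do the two readings differ?** Take Grade 3 neutropenia with ANC below 1000/mm³ and fever as the only sign:

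| Temperature | 38.5°C as cut-off | Bracketed example |
|---|---|---|
| Single reading below 38.3°C, not sustained | Not met | Not met |
| Single reading 38.3 to 38.5°C | Not met | DLT |
| 38.0 to 38.5°C for more than one hour | Not met | DLT |
| Above 38.5°C | DLT | DLT |

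The conflict covers 38.5 − 38.3 = 0.2°C for a single reading and 38.5 − 38.0 = 0.5°C for a sustained one. The single-reading band assumes that 38.3°C means that value or higher; the text as read shows no comparison sign there.

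**3. What else would make the event a DLT?**

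- Grade 4 neutropenia with any clinical symptom falls outside its exemption, so the conflict matters mainly for Grade 3.
- Section 6.6.2 counts treatment with growth factors in the DLT period as a DLT. Section 6.5.2 is softer and says only that therapeutic use may be one.
- An AE that prevents delivery of 80% of the planned dose is a DLT. With 21 daily doses, 17/21 = 81% and 16/21 = 76%, so five doses must be missed. This route is not fully independent, because interruption in the DLT period is mandatory only for an AE already judged to meet DLT criteria.

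**4. Would drug be stopped anyway?** Section 6.6.2.1 also says to interrupt for Grade 3 drug-related toxicity, and the AESI table points to Table 10, which covers Grade 3 hematologic reactions. However, that paragraph opens by addressing dose modifications outside the DLT period, so its reach inside the period is arguable. The AESI table itself lists interruption only as one option.

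**5. Does a missed site flag reach the dose models?** Not by itself. The models take DLTs as identified by the SMC, and the event reaches the Sponsor as an AESI within 24 hours. That report makes the event visible but does not classify it, and the SMC would apply the same bullet.

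**The case against.** The strongest reply is that the bullet already points one way. The operative condition is Grade 3 or higher neutropenia with clinical signs or symptoms. The 38.5°C figure follows *such as*, so it illustrates and does not limit, and the bracket names the lower-temperature events as instances. To exclude them, a reader must turn an illustration into a threshold and ignore a named example. This stands as the better reading, and it is also the safer one. It does leave the 38.5°C figure with no function, which is why a careful site could still take it as the cut-off.

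The safeguards also largely stand. AESI reporting, possible Sponsor assessment, SMC confirmation and the SMC's power to add DLTs protect the modelled endpoint. The SAP shows investigator and SMC classifications side by side, so a discrepancy would be visible. If escalation went ahead early, the SMC must in any case consider the last participant's later data at a subsequent meeting. None of these provisions states which temperature governs. The SMC's power to add a DLT also rests on a different test, unacceptable risk from further escalation.

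A reader might infer that the protocol excludes febrile neutropenia between 38.0 and 38.5°C from the DLT definition, or that DLTs are being undercounted. The text does not support the first, because it names those events as examples. Nothing in the documents shows the second, because no such case is reported.

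**Conclusion.** The bullet is inconsistent as written and should be corrected, but the point is minor. The realistic failure is a site that does not flag, and does not interrupt for, Grade 3 neutropenia with a single reading of about 38.3 to 38.5°C or a sustained 38.0 to 38.5°C.

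A reader might also infer a shift in the recommended dose or the MTD. The documents cannot support this. The prior is redacted in Section 9.4.2.1 and Appendix 12, and no rate is given for the event. Running the model on assumed priors would show what any one extra DLT does, not how often this wording produces or hides one. Model recommendations are also not binding on the SMC.

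The conclusion assumes that a comparison sign at 38.3°C may have been lost when the text was read. It also assumes that the SMC Charter, which is not among the documents, does not already settle the threshold.

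**What to change.** In Section 6.6.2, delete the 38.5°C figure and keep the bracketed febrile-neutropenia definition as the single fever rule. Possible wording: *Grade ≥ 3 neutropenia with clinical signs or symptoms, including febrile neutropenia, defined as ANC < 1000/mm³ with either a single temperature at the 38.3°C limit (sign as in the source) or ≥ 38°C for more than one hour.*

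Alongside this:

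- Check the comparison sign at 38.3°C against the source document.
- Use the same wording for the DLT flag on the AE CRF page.
- Re-check any Grade 3 neutropenia with fever that has already been classified.

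The cost is one line in the next amendment, with a clarification in the SMC Charter until then if it does not already set a rule. The downside is that a few more events may count as DLTs.

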6.6.2.1 Dose Interruptions and Modifications

Participants who experience an AE meeting DLT criteria during the DLT assessment period need to interrupt M4076 (Table 10). No dose modifications of M4076 should be made during the DLT assessment period for the dose escalation part of the study (Part 1A).

Participants who experience rash and systemic symptoms (e.g., fever, vomiting, diarrhea), or other signs of hypersensitivity should have M4076 discontinued immediately and are not to be rechallenged with any dose of M4076. Grade 2 and Grade 3 rash (without systemic symptoms) should be managed with treatment interruption and supportive medications, including topical or oral steroids.

Dose modifications outside the DLT period are allowed. Participants who experience a Grade 4 drug-related toxicity should discontinue treatment promptly. For a Grade 3 drug-related toxicity, M4076 treatment should be interrupted and may resume at a reduced dose provided the toxicity has resolved to Baseline value or Grade ≤ 1 within 2 weeks. At the first instance of a Grade 3 toxicity, study intervention will be held, and allowed to resume with a 25% dose reduction once said toxicity recovers to Grade ≤ 1 . Should a study participant develop a recurrent Grade 3 drug-related toxicity, study intervention will once again be held, and allowed to resume with a 50% dose reduction once said toxicity recovers to Grade ≤ 1 . Subsequent recurrences of Grade 3 toxicity will prompt discontinuation of study treatment, i.e., no more than 2 dose reductions will be permitted. Based on emerging data (i.e. toxicity, PK, Pd) and tablet strength availability, different dose reductions may be recommended as agreed between Sponsor and investigator, such as alternative dose reduction steps or different dosing regimen. Recommended dose reductions for each potential DL are provided in [Table 10](#).

Once the dose of M4076 has been reduced in an individual participant, it must not be escalated back to the original dose level. If more than 2 dose reductions of $> 50\%$ dose decrease are indicated, the participant will be permanently discontinued from study intervention. Consultation between Investigator and Sponsor about dose reduction is encouraged.

Table 10 M4076 Recommended Dose Modifications for Grade 3 Hematologic and Nonhematologic ADRs

Potential DLs – Starting doses	Grade 3 Hematologic and Nonhematologic ADRs		
	1 st occurrence DR of 25%	2 nd occurrence DR of 50%	3rd occurrence
100 mg	50*	Discontinued	NA
200 mg	150	100	Discontinued
300 mg	200	150	Discontinued
400 mg	300	200	Discontinued
600 mg	450	300	Discontinued

ADR = adverse drug reaction; DL = dose level; DR = dose reduction; NA = not applicable.

* reduction is 50% based on available tablet strengths.

For delays in study intervention exceeding 2 weeks, the intervention will be permanently discontinued, except for a situation where the participant has benefitted from study intervention with M4076 before the administration delay and is expected to continue to benefit from resumed study intervention after the interruption.

See Section 7 for information regarding discontinuation of study intervention and participant discontinuation/withdrawal.

6.7

Study Intervention after the End of the Study

Participants still benefitting from study treatment will be offered continued access to the treatment they received during the study after the end of the study, when appropriate, within defined limitations and as described below.

A roll-over study or Single Patient Post-study Access may be implemented. Under this mechanism, individual participants who completed the study may be provided with their assigned treatment outside of the clinical study under the responsibility of the treating physician. This treatment should comply with any legal and regulatory requirement as there are no appropriate alternative treatments available.

Data on safety events continue to be collected per a safety reporting agreement with the participants treating physician.

The Sponsor will not provide any additional care to participants after they leave the study because such care would not differ from what is normally expected for patients with advanced solid tumors.

7

Discontinuation of Study Intervention and Participant Discontinuation/Withdrawal

7.1 Discontinuation of Study Intervention

The participant must be withdrawn from study intervention in the event of any of the following:

- At his/her request (withdrawal of consent of study intervention).
- Development of unacceptable toxicity.
- Occurrence of progressive disease according to RECIST 1.1 ([Appendix 9](#)). Study intervention may continue past the determination of progressive disease if deemed indicated by the Investigator and discussed with the Sponsor.
- Initiation of any other anticancer therapy, except for palliative radiation therapy (see Section [6.5.4](#)).
- Occurrence of an exclusion criterion that is clinically relevant and affects the participant's safety, if discontinuation is considered necessary by the Investigator and/or Sponsor.
- Occurrence of pregnancy.
- Use of a nonpermitted concomitant drug (including any other drug with known anticancer activity unless specified otherwise).
- Noncompliance that is deemed by the Investigator or the Sponsor to compromise participant safety or study integrity.

In rare instances, it may be necessary for a participant to permanently discontinue (definitive discontinuation) study intervention. If study intervention is definitively discontinued, the participant will remain in the study to be evaluated for an End of Study Intervention Visit. The Schedule of Activities indicates data to be collected at the time of discontinuation of study intervention and follow-up and for any further evaluations that need to be completed.

Pregnancy:

For information regarding pregnancy, see Section [8.3.5](#).

The Schedule of Assessments specifies the data to collect at study intervention discontinuation and follow-up, and any additional evaluations that need to be completed.

7.2 Participant Discontinuation/Withdrawal from the Study

- A participant may withdraw from the study at any time, at his/her own request or may be withdrawn at any time at the discretion of the Investigator for safety, behavioral compliance, or administrative reasons.
- At the time of discontinuing from the study, if possible, a discontinuation visit will be conducted, as listed in the Schedule of Activities. The Schedule of Activities specifies the data to collect at study discontinuation and follow-up, and any additional evaluations that need to be completed.

- If the participant withdraws consent for future involvement in the study, any data collected up to that point may still be used, but no future data can be generated, and any biological samples collected will be destroyed.
- A participant has the right at any time to request destruction of any biological samples taken. The Investigator will document this in the site study records.

Additional participants may be enrolled for each participant who withdraws from the study after signing consent and successfully meeting entry criteria but did not receive study intervention. Additionally, participants excluded from the DLT analysis set may be replaced.

The Investigator will be responsible for the safety of the study participants and make every attempt to collect data. See Section 7.3 for further details.

7.3 Lost to Follow-Up

A participant will be considered lost to follow-up if he or she repeatedly fails to return for scheduled visits and is unable to be contacted by the study site.

The following actions will be taken if a participant fails to return to the clinic for a required study visit:

- The site will attempt to contact the participant and reschedule the missed visit as soon as possible, counsel the participant on the importance of maintaining the assigned visit schedule and ascertain if the participant wants to or should continue in the study.
- Before a participant is deemed “lost to follow-up”, the Investigator or designee will make every effort to regain contact with the participant: 1) where possible, make 3 telephone calls; 2) if necessary, send a certified letter (or an equivalent local method) to the participant’s last known mailing address, and 3) if a participant has given the appropriate consent, contact the participant’s general practitioner for information. These contact attempts will be documented in the participant’s medical record.
- If the participant continues to be unreachable, he/she will be deemed as “lost to follow-up”.

8 Study Assessments and Procedures

- Study assessments and procedures and their timing are summarized in the Schedule of Activities.
- No protocol waivers or exemptions are allowed.
- Immediate safety concerns are discussed with the Sponsor immediately upon occurrence or awareness to determine if the participant should continue or discontinue study intervention.
- Adherence to the study design requirements, including those specified in the Schedule of Activities, is essential and required for study conduct.
- All screening evaluations will be completed and reviewed to confirm that potential participants meet all eligibility criteria. The Investigator will maintain a screening log to

record details of all participants screened, to confirm eligibility, and if applicable, record reasons for screening failure.

- Prior to performing any study assessments that are not part of the participant's routine medical care, the Investigator will obtain written informed consent as specified in [Appendix 2](#).
- Procedures conducted as part of the participant's routine medical care (e.g., blood count) and obtained before signing of the ICF may be used for screening or baseline purposes provided the procedures met the protocol-specified criteria and were performed within the time frame defined in the Schedule of Activities.

